8.3 Exclusion Criteria

Subjects meeting any of the following criteria will be *excluded* from the study:

- Have had prior axillary surgery or ipsilateral radiation in the breast(s) that is planned for this procedure.
- Advanced breast cancer subjects with stage IIB, III or IV.
- Known allergy or history of adverse reaction to ICG, iodine or iodine dyes.
- Subjects who have participated in another investigational study within 30 days prior to surgery.
- Pregnant or lactating subjects.
- Subjects who, in the Investigator's opinion, have any medical condition that
 may make the subject a poor candidate for the investigational procedure, or
 interferes with the interpretation of study results.

8.4 Withdrawal of Subjects

Subjects can voluntarily withdraw (or be withdrawn) at any time during the study. Investigators may withdraw a subject from the study due to:

- A new health condition, diagnosis or finding appears that is suspected to require care or medication prohibited by the protocol.
 - e.g. the planned surgical procedure is modified to a procedure prohibited by the protocol.
- The subject has intolerable adverse events.
- It is in the subject's best interest according to the Investigator's clinical judgment.

If a subject is prematurely withdrawn from the study, the reason(s) for withdrawal must be recorded on the relevant page of the subject's Study Completion CRF.

Subjects who discontinue the study prematurely will not be replaced. The Sponsor may stop the study at any time.

9. SUBJECT ENROLLMENT AND SUBJECT IDENTIFICATION PROCEDURES

9.1 Subject Enrollment

Enrollment will occur on the day of surgery. Prior to surgery, the subject will have provided written informed consent, completed all baseline procedures and met all the requirements of inclusion and exclusion. Enrollment should be performed as closely as possible to the surgical procedure to minimize the incidence of dropout. Enrollment is completed only after verification of proper informed consent and study eligibility.

9.1.1 Subject Enrollment Procedure

Since this study is a single arm design, randomization is not required. In the FILM-B study, each subject will serve as their own control. All subjects enrolled will receive the same study treatment, which is lymphatic mapping using IC2000/SPY-PHI and Tc99/Gamma Probe during sentinel lymph node biopsy. This will allow for a direct, non-inferiority comparison of IC2000 and SPY-PHI to Tc99 and Gamma Probe in lymphatic mapping and identification of LNs during SLNB in subjects with early stage breast cancer. The study coordinator or designee will verify that the subject is eligible and that informed consent has been obtained prior to initiating the enrollment process. Once complete, the study coordinator or designee will assign the subject an Enrollment ID Number and the subject will be considered enrolled in the trial. The study coordinator will then disclose to the Investigator that the enrollment process is complete.

A subject cannot receive study treatment until the enrollment process has been completed. The enrollment procedure should not be initiated unless the study coordinator or designee verifies the baseline information and confirms that the subject is eligible. If any deviations occur (errors such as assigning incorrect enrollment), the clinical site will be required to contact the Sponsor and wait for guidance on how to proceed.

If, at any time after enrollment, the subject becomes ineligible or withdraws, the subject will be categorized with respect to the definitions outlined for the analysis populations (see Section 14, Statistical Methods).

9.2 Subject Identification

10. STUDY TREATMENTS

10.1 Device Descriptions

10.1.1 SPY Portable Handheld Imaging (SPY-PHI) System

SPY-PHI is an imaging system used in capturing and viewing fluorescent images for the visual assessment of blood flow, as an adjunctive method for the evaluation of tissue perfusion, and related tissue-transfer circulation in tissue and free flaps used during various surgical procedures.

SPY-PHI consists of the following components:

- An Open Field Handheld Imaging Head (with an integrated Light Guide cable), and the Video Processor/Illuminator (VPI).
- SPY-PHI PAQs containing the imaging agent, Water for Injection or aqueous solvent, and sterile drapes

The SPY-PHI System provides full color visible light and NIR fluorescence video imaging for intraoperative visual assessment of blood vessels and related tissue perfusion.

SPY-PHI has a 510(k) clearance from the FDA (K200737) for the following indications for use:

"

Upon intravenous administration of SPY AGENT™ GREEN (indocyanine green for injection, USP) the SPY-PHI System is used with SPY AGENT™ GREEN to perform intraoperative fluorescence angiography. The SPY-PHI System is indicated for use in adult and pediatric patients one month of age and older.

The SPY-PHI System is indicated for fluorescence imaging of blood flow and tissue perfusion before, during, and after: vascular, gastrointestinal, organ transplant, and plastic, micro- and reconstructive surgical procedures.

Upon interstitial administration of SPY AGENT™ GREEN, the SPY-PHI System is used to perform intraoperative fluorescence imaging and visualization of the lymphatic system, including lymphatic vessels and lymph nodes."

SPY-PHI is also licenced in Canada with the following intended use:

Upon intravenous administration of SPY AGENT™ GREEN (Indocyanine green for injection, USP) the SPY-PHI System is used with SPY AGENT™ GREEN to perform intraoperative fluorescence angiography.

The SPY-PHI System is indicated for fluorescence imaging of blood flow and tissue perfusion before, during, and after: vascular, gastrointestinal, organ transplant, and plastic, micro- and reconstructive surgical procedures.

Examples of its use for near-infrared fluorescence imaging before, during and after various procedures include, but are not limited to, coronary bypass surgery, organ transplant procedures, plastic and reconstructive surgery such as breast reconstructive procedures and micro-surgery (including plastic reconstructive surgery utilizing autologous flaps), renal cancer surgeries, vascular surgeries (such as wound, amputation and coronary vessels), myocardial perfusion in cardiac and cardiovascular surgeries, GI surgeries and parathyroid perfusion during endocrine surgery.

Please refer to the SPY-PHI Operator's Manual for a full description and specifications of the system³⁸. In this study, the use of IC2000 and SPY-PHI for visual identification of LNs is investigational.

10.2 Imaging Agent Description

10.2.1 IC2000 for Injection (ICG for Injection, USP)

10.2.1.3 Chemistry and Manufacturing

IC2000 was manufactured in full compliance with the FDA's current Good Manufacturing Practice (cGMP) for Finished Pharmaceuticals (21 CFR Part 211) and meets all cGMP requirements for Health Canada.

10.2.1.4 Labelling of IC2000

IC2000 is labeled according to US and Canadian regulatory requirements with the following information:

- IC2000 (indocyanine green for injection, USP), 25 mg lyophilized ICG
- Sterile
- Protocol No.: SPY LNM 01
- Directions for use: Refer to Clinical Protocol
- Store at: 20–25°C (68-77°F)
- Lot: xxxxxxxxx
- EXP: Mmm-YYYY
- CAUTION New drug Limited by Federal (or United States) law to investigational use.
- Investigational drug to be used only by a qualified investigator.
- Sponsor: Novadaq Technologies ULC. [name]. [name]

10.2.1.5 Packaging and Distribution of IC2000

IC2000 will be packaged into investigational FILM-B SPY-PHI Cases which contain 6 SPY-PHI Kits as described below and distributed by the study Sponsor (NOVADAQ). Each FILM-B SPY-PHI Kit is indicated for use exclusively with the SPY-PHI System, and should only be used for the purposes of this study (see also Section 17.1.2, Study Supplies).

Each FILM-B SPY-PHI Kit contains:

[figure not shown]
- One single use 25 mg vial of sterile IC2000 for Injection, USP
- One single use 10 ml vial sterile Water for Injection
- One SPY-PHI Sterile Drape
- 10 ml syringes, sterile
- 1 ml Tuberculin syringe, sterile
- 30G, 0.75 inch needle, sterile

All information included on the IC2000 for Injection vial labels will appear on the FILM-B SPY-PHI Kit labels along with a description of the contents of the kit. Each kit will bear a unique serial number and will meet regulatory requirements necessary for each participating country.

10.2.1.6 Storage and Administration of IC2000

FILM-B SPY-PHI Cases and Kits which contain IC2000 will be stored at 20°C to 25°C (68° to 77°F) in a secure locked area, accessible to authorized personnel only. FILM-B SPY-PHI Cases and Kits will be stored, and the IC2000 will be handled, prepared and administered by qualified, trained personnel only as described in Section 12.3.2, Imaging Agent Dosing and Administration of IC2000.

10.3 Installation, Training and Storage

10.4 Concomitant Treatment

11. RISKS / PRECAUTIONS

Refer to the SPY-PHI Operator's Manual for a full description of the risks and precautions associated with all components of the SPY-PHI respectively. The entire SPY-PHI Operator's Manual should be read before using the device³⁸. Failure to follow the instructions and warnings in the manual may result in unsafe operation of the system and/or injury to the subject or operator.

11.1 SPY-PHI System

SPY-PHI is classified by the United States FDA as a Class II medical device with a Product Code of OWN. SPY-PHI, for the purposes of fluorescence angiography, is not identified as a significant risk device on the FDA Information Sheet titled "Significant Risk and Non-significant Risk Medical Device Studies".

The use of the SPY-PHI for LN identification and mapping is investigational. SPY-PHI should only be used in accordance to their approved Indication for Use or in accordance to the study procedures described in this protocol.

11.2 IC2000 (Indocyanine Green for Injection, USP)

[figure not shown]
IC2000 will be injected intradermally into the peri-areolar area of the breast, and in subjects with occluded or blocked lymphatic vessels ICG will be injected intradermally

12. STUDY PROCEDURES

12.1 Schedule of Events

Table 3 Schedule of Events

12.2 Baseline/Screening Procedures (Day -30 to Day 0)

After signing the informed consent form, subjects will be assigned a screening number (see Section 9.2, Subject Identification) and be evaluated for eligibility into the study.

The following procedures will be conducted during the baseline assessment:

12.3 Day 0 Procedures

As per standard of care, all subjects will receive an injection of Tc-99m either the day before or the morning of surgery.

Subjects are considered enrolled after verification of proper informed consent and eligibility, just prior to the time of injection of IC2000, at the start of surgery while the subject is in the operating room and under anesthesia (see below for administration procedures).

For mapping procedure details, refer to Section 7.3.1.2, Visual Identification and Mapping Procedure.

All subjects will undergo the appropriate surgical procedure according to the surgeons and/or hospitals standard practice for breast cancer surgery. The surgical procedures will include either a lumpectomy or a mastectomy.

[figure not shown]
All subjects will receive the hospital/institutions and surgeons standard pre-operative and post-operative care with the addition of any study specific requirements.

All subjects will have total blood loss recorded at the completion time of surgery as per standard of care.

Either during or immediately post-operatively, the details of the SLNB procedure and surgical procedure will be documented. LN mapping data will be collected including the ability to visualize lymphatic vessels and identify LNs as well as data to confirm the safety of intradermal injection of IC2000. In subjects in whom lymphatic flow through the lymphatic vessels may be occluded or damaged proceed to alternate route of administration of IC2000 and map with SPY.

Failed mapping is defined as no LNs detected by either Tc99m and Gamma Probe, IC2000 and SPY or LNs deemed clinically suspicious.

LNs identified during the mapping procedure will be classified according to Section 7.4, Classification of LNs, and recorded in the CRFs.

12.3.2 Imaging Agent Dosing and Administration of IC2000

The IC2000 solution will be prepared and administered by the appropriate qualified study investigator or operating room personnel. The breast(s) will be injected with IC2000 at the start of surgery.

See Section 7.3.1.1, Injection Technique, for specifics.

12.3.3 Visualization of Lymphatic Vessels and Identification of LNs during Lymphatic Mapping

IC2000 and SPY-PHI (Fluorescent Only) identification criteria:

 LNs identified with NIR fluorescence signal using IC2000 and SPY-PHI invivo, not confirmed as "hot" ex-vivo with Tc-99m and Gamma Probe.

IC2000/SPY PHI and Tc-99m radioactive colloid with gamma probe identification criteria (Both):

 LNs identified with NIR fluorescence signal using IC2000 and SPY-PHI in-vivo and confirmed with Tc-99m and Gamma Probe as "hot" utilizing the 10 second count, ex-vivo (LN must be 10% or more of the "hottest" node).

Tc-99m radioactive colloid with Gamma Probe identification criteria (Tc99m only):

- LNs identified in-vivo with Tc-99m and Gamma Probe as "hot" LNs, with no NIR fluorescence signal using IC2000 and SPY-PHI (LN must be 10% or more of the "hottest" node).
- LNs identified in-vivo by Tc-99m/Gamma Probe only, which upon reassessment with IC2000/SPY are determined to be fluorescent, will be classified by the investigator as "Tc-99m only" LNs (LN must be 10% or more of the "hottest" node).

Clinically suspicious identification criteria (Fluorescent and Tc99 negative):

 Clinically suspicious LNs designated as palpable masses will be excised regardless of visible fluorescence or if deemed 'hot' with a Gamma Probe.

All LNs identified by IC2000/SPY-PHI and Tc-99m/Gamma Probe will be classified *ex-vivo* or *in-vivo* by the investigator:

- 1. Fluorescent only
- 2. Tc99m only
- 3. Both (Fluorescent and Tc99m positive)
- 4. Clinically suspicious (Fluorescent and Tc99 negative)

12.4 Post-operative Follow-up Visits (Day of discharge to Day 30)

Subjects will have standard of care assessments throughout the study according to the hospital/institution's standard procedures as well as study specific visits on the date of

discharge and Day 30 (±7 days). Day 30 visit will be a telephone call and subjects will be assessed for the following throughout the study:

- Concomitant medications and procedures as described in Section 10.4, Concomitant Medication.
- Adverse events and adverse device effects according to Section 13.1, Evaluation, Recording and Reporting of Adverse Events.

12.5 Histopathology of Excised LN

The presence of lymphoid tissue for each excised LN will be confirmed by tissue analysis.

All LNs will be routinely sectioned and stained with pathology assessment as per the hospital/institutions standard procedure.

12.6 Image Acquisition and Transmission

13. EVALUATION, RECORDING, AND REPORTING OF ADVERSE EVENTS

All untoward medical occurrences either observed by the Investigator or one of his/her medical collaborators, or reported by the subject spontaneously, or in response to the direct question below, will be reported as follows:

- All events occurring before injection of Tc-99m should be recorded in the source documents and will be considered part of the subject's medical history.
- All adverse events occurring during the study will be recorded as adverse events on the adverse event CRF.
- Events occurring as a result of the surgery will be reported as adverse events related to the surgical procedure in the adverse event CRF.
- Events related to SPY-PHI will be recorded as adverse device effects in the adverse event CRF.

- Events that are not related to SPY-PHI shall be recorded as adverse events.
- Events related to SPY-PHI that affect a user of the device (non-subject) are recorded as technical complaints.
- Events related to IC2000 and/or Tc99m will be recorded as adverse events related to IC2000 and/or Tc99m in the adverse event CRF.

[figure not shown]

AEs reported on the CRF will include the date of onset, severity, relationship to SPY-PHI, IC2000 and/or Tc99m, relationship to surgical procedure, date of resolution (or the fact that it is ongoing or has become chronic), action taken, and whether the AE is serious or not.

AEs will be coded using MedDRA and graded according to the National Institutes of Health and National Cancer Institute's Common Terminology Criteria for Adverse Events (CTCAE), v5.0: November 27, 2017 (see Appendix 1).

13.1 Definitions

13.2 Adverse Event Descriptions

Intensity

The intensity of AEs, including ADEs will be characterized as mild, moderate, severe, life-threatening or fatal as follows:

Mild Asymptomatic or mild symptoms; clinical or diagnostic observations

only; intervention not indicated.

Moderate Minimal, local or noninvasive intervention indicated; limiting age

appropriate instrumental activities of daily living.

Severe Severe or medically significant but not immediately life-threatening;

hospitalization or prolongation of hospitalization indicated; disabling;

limiting self care activities of daily living.

Life-threatening Life-threatening consequences; urgent intervention indicated.

Death related to AE.

Relationship

13.3 Reporting and Evaluation of Serious Adverse Events and Unanticipated Adverse Device Effects

Any SAE or UADE occurring in this study must be reported immediately (within 24 hours of discovery) by email to the contact listed below:

SAEs and UADEs will be reported to the Institutional Review Board (IRB)/Ethics Committee (EC) according to the institution's policies, but within 10 days of occurrence.

The Sponsor will be responsible for reporting SAEs/UADEs to the FDA or Health Canada in accordance with federal regulatory requirements.

The Sponsor will provide documentation of reportable events to the Investigator.

13.4 Follow-up for Adverse Device Effects and Adverse Events

[figure not shown]
Throughout the study until the final study visit contact, ADEs will be followed until they resolve or become chronic. All AEs will be followed throughout the study until the Day 30 visit. All AEs related to IC2000, SPY-PHI, Tc99m or the mapping procedures, as determined by the Investigator, will be followed until resolution or deemed chronic.

At the final study visit, new AEs, as well as follow-up information for continuing AEs, will be recorded in the CRF and source document. If an SAE or UADE is unresolved at the final study visit, it will be followed by the Investigator until it resolves or becomes chronic (as judged by the Investigator). Follow-up data for such SAEs will be recorded in the source document and reported to the safety contacts. Non-serious ongoing AEs will be followed beyond the final study visit if they are related to the study procedures at the discretion of the Investigator.

13.5 Reporting of Technical Complaints / Device Deficiencies

13.6 ADEs Technical Complaints / Device Deficiencies that are UADEs

14. STATISTICAL CONSIDERATIONS

14.1 Analysis PopulationsPer-protocol (PP)

Since this is a non-inferiority design, the PP analysis population will be primary; it will comprise all subjects that: (1) meet all eligibility criteria; (2) received the full dose of tracer / dye; (3) successfully completed the mapping procedure (i.e. have at least one lymph nodes detected *in-vivo* by IC2000 and SPY or by Tc99m and Gamma Probe, or have lymph nodes deemed clinically suspicious), and; (4) have histology confirmed lymph nodes.

Modified Intent to treat (mITT)

The mITT analysis population will comprise all enrolled subjects who received at least one injection of IC2000 and Tc99. All subjects meeting this criterion will be included in the mITT population regardless of whether or not (1) they received lymphatic mapping (i.e. they only had LNs identified through palpation), or (2) received the full dose of tracer / dye. Subjects who have the mapping procedure aborted due to circumstances, such as a higher stage cancer than initially expected, subjects with failed mapping, or subjects without histology confirmed lymph nodes will not be included in the mITT. The mITT population will be used for a secondary analysis of the primary endpoint.

Safety

The safety analysis population will comprise all subjects enrolled in the study who received at least one injection of IC2000 regardless of whether LN mapping was initiated or was successful. All safety endpoints, including the summary of AEs or ADEs in the trial, will be analyzed using this analysis population.

14.2 Demographic and Baseline Characteristics

The demographic and baseline characteristics will be described for the mITT and PP populations with summary statistics including the mean, standard deviation, median, minimum and maximum for continuous variables, and counts and percentages for categorical variables.

The following parameters will be summarized: age, race, body mass index, cancer stage and grade, vital signs, surgical predictive factors, and medical history.

14.3 Primary Objective

To assess the effectiveness of IC2000/SPY during lymphatic mapping and sentinel lymph node biopsy, the proportion of excised lymph nodes identified by IC2000/SPY in-vivo and confirmed by histology (\mathbf{Q}_{T}) will be compared with the proportion of excised lymph nodes identified with Tc99m/Gamma and confirmed by histology (\mathbf{Q}_{C}). The denominator for both \mathbf{Q}_{T} and \mathbf{Q}_{C} will be the total number of lymph nodes identified and excised that were confirmed by histology, inclusive of clinically suspicious lymph nodes.

The following hypothesis will be tested at the lymph node level:

H0:
$$Q_T \le Q_C - 0.05$$
 H1: $Q_T > Q_C - 0.05$

To test this hypothesis, the difference \mathbf{Q}_{T} - \mathbf{Q}_{C} will be calculated and the associated two-sided 95% confidence interval. If the lower bound of the interval is greater than -0.05, non-inferiority (using the PP population) will be claimed.

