2.8 Sample Size and Statistical Analysis

This is a prospective, open label, multicenter, non-inferiority within-patient study to determine the effectiveness of IC2000 (Indocyanine Green (ICG) for Injection) and the SPY Portable Handheld Imaging System (SPY-PHI) as an intraoperative fluorescence visualization tool, in the visual identification of lymphatic vessels and LNs including LNs during lymphatic mapping and SLNB procedures as confirmed by Tc99m and Gamma Probe. A sample size of 356 LNs contributed by approximately 137 evaluable patients will be required using the following assumptions:

- 1. The average detection rate with Tc99m and Gamma Probe will be 91.6%.
- The average detection rate with IC2000 and SPY will be 96%.
- A power of 90%.
- 4. A non-inferiority margin of 5 percentile units.
- An average of 2 LNs is expected to be excised per patient.

Estimating that 6% of patients will be excluded from the per-protocol (PP) population (see section 14.1), approximately 379 LNs are required.

Additional details are included in Section 14.7, Sample Size Considerations.

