14.7 Handling of Missing Data

14.8 Sample Size Considerations

This is a single arm, non-inferior, sequential design, paired comparison study of IC2000 and SPY with the standard of care, Tc99m/Gamma Probe in the identification of lymph nodes during lymphatic mapping and sentinel lymph node biopsy. The sample size calculation for the primary endpoint was performed using nQuery Advisor® 7.0 (Copyright® 1995-2007, Statistical Solutions Ltd). To support the sample size calculation, the average LN detection rate with IC2000 and SPY (Q_T) of 96% was assumed, based on the recent meta-analyses; Mok et al. 56 An average detection rate of 91.6% has been assumed for Tc99m and Gamma Probe (Q_C) 57 A 5% non-inferiority margin is deemed to be conservative for sentinel lymph node biopsy (SLNB).

Assuming an average of 2 excised LNs per patient evaluated by both methodologies with 11.2% discordance $\frac{57}{1}$, 137 subjects would be required to prove the non-inferiority of IC2000 and SPY with a non-inferiority margin of 5% using a one-sided 2.5% alpha and 90% power. A 1.0% Q_T advantage would establish non-inferiority.

Lower one-sided 97.5% confidence bound: Difference in paired proportions (simulation)

	90% Power	1-sided p=0.025
Confidence level, 1-α (one-sided)	0.975	0.975
Expected difference, $Q_T - Q_C$, Δ	0.044	0.01
Proportion discordant, $d = q_{10} + q_{01}$	0.112	0.112
Proportion both yes, q ₁₁	0.883	0.883
Lower limit for Q _T - Q _C , LL	-0.050	-0.050
Number of simulations	1000	1000
Random seed for simulations	123	123
Power (%)	90	NA
n (number of paired evaluations)	137	137

Based on a 2-level hierarchical model in which nodes are nested within subjects, and given that we expect an average of 2 nodes to be excised per patient the aforementioned sample size needs to be multiplied by an inflation factor (IF), aka Design Effect (DEFF $\frac{54,55}{}$), of 1+(n-1)*ICC where n is the average sample size per cluster and ICC (expected to be at most 0.1) is the intra-class correlation: IF = 1+ (2x2 – 1) x 0.1 = 1.3, where n was multiplied by 2 due to the fact that LNs will be identified using 2 different methods. Based on a total of 274 LNs and an IF of 1.3, a sample size of 356 lymph nodes will be required. Estimating that 6% of patients will be excluded from the per-protocol (PP) population (see Section 14.1), approximately 379 LNs are required.

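### Non-inferiority is decided on the per-protocol set alone, but in this paired design that set is not guaranteed to be the conservative one, so the mITT bound should also have to pass

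*Combined protocol and SAP*

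**What the plan says.** Section 14.1 chooses the primary set with one reason: "Since this is a non-inferiority design, the PP analysis population will be primary". To be in PP, a subject must be eligible, have had the full dose of tracer / dye, have completed mapping with at least one node found, and have histology-confirmed nodes.

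The mITT set needs at least one injection of each agent and does not need the full dose. It leaves out aborted mapping, failed mapping and subjects without confirmed nodes. Its role is limited: "The mITT population will be used for a secondary analysis of the primary endpoint".

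The decision rule in 14.3 uses PP only: "If the lower bound of the interval is greater than -0.05, non-inferiority (using the PP population) will be claimed". Both detection rates share one denominator, all excised histology-confirmed nodes. Under 12.3.3, a hot node without fluorescence is Tc99m only, so it counts for the gamma probe and not for IC2000.

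No visible text gives mITT a success criterion or says what follows if the two sets disagree.

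**The concern.** PP is usually preferred in a two-arm non-inferiority trial because deviations tend to make the arms look alike, which makes non-inferiority easier to show in the full set. Here each subject is their own control (9.1.1) and each node is scored by both methods. If one tracer is under-dosed and misses a node that the other finds, the miss counts against the under-dosed tracer only. The difference moves away from zero, towards the tracer that was fully given.

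Excluding incomplete-dose subjects can therefore help either method. If the excluded nodes are mainly IC2000 misses, PP flatters IC2000. If they are mainly Tc99m misses, PP is the stricter set. The reason given in 14.1 does not establish that PP is conservative, yet PP alone decides the claim, and an mITT bound below -0.05 could not block it.

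**Working it through.** **Inputs.** From 2.8: "The average detection rate with Tc99m and Gamma Probe will be 91.6"% and "The average detection rate with IC2000 and SPY will be 96"%, so the planned difference is 0.96 - 0.916 = +0.044. From 14.8: discordance 0.112, margin 0.05, inflation factor 1.3, and "using a one-sided 2.5% alpha and 90% power". Hence fluorescent-only = (0.112 + 0.044)/2 = 0.078 and Tc99m-only = (0.112 - 0.044)/2 = 0.034.

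**The plan's own figures.** The closed form (1.96 + 1.2816)² × (0.112 - 0.044²)/0.094² gives 131 pairs. The plan used simulation. At 137 pairs, score-type paired intervals give simulated power of 89.4% to 90.3%, so 137 reproduces. Then 274 × 1.3 = 356.2 and 356/0.94 = 378.7, which match 356 and 379 nodes.

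**How far the sets can differ.** From 14.8: "Estimating that 6% of patients will be excluded from the per-protocol (PP) population". This gives 379 - 356 = 23 nodes. It is an upper bound on the nodes that are in mITT but not in PP, because the 6% also covers failed mapping and no confirmed histology, and those subjects are in neither set. What remains is mainly ineligible and incomplete-dose subjects. The documents give no count of them, so I also show 12 and 6 nodes as assumed values.

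**When PP passes and mITT fails.** 14.3 names no interval method, so I use a Wald interval with the variance multiplied by 1.3: lower bound = D - 1.96 × √(1.3 × (d - D²)/n), where D is the difference and d the discordance. PP has n = 356 and d = 0.112. Suppose k of the extra nodes are Tc99m-only and the rest are concordant (assumption).

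For a PP difference of 0:
- PP bound: 0 - 1.96 × √(1.3 × 0.112/356) = -0.040, a pass.
- k = 4 of 23: D = -4/379 = -0.0106, d = (39.87 + 4)/379 = 0.1158, bound -0.0496, a pass.
- k = 5 of 23: D = -5/379 = -0.0132, d = (39.87 + 5)/379 = 0.1184, bound -0.0527, a fail.

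| Observed PP difference | PP bound | k needed, 23 extra nodes | 12 extra | 6 extra |
|---|---|---|---|---|
| 0 | -0.040 | 5 | 4 | 4 |
| +0.010 | -0.030 | 8 | 7 | cannot fail |
| +0.020 | -0.020 | 11 | 10 | cannot fail |
| +0.044 | +0.005 | 18 | cannot fail | cannot fail |

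Without the inflation factor, the 23-node counts are 6, 9, 12 and 20.

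**Opposite direction.** If all 23 extra nodes are fluorescent-only, as after incomplete Tc-99m dosing, a PP difference of 0 gives mITT D = 23/379 = 0.0607, d = (39.87 + 23)/379 = 0.1659 and bound +0.014. PP, at -0.040, is then the stricter set.

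**Power of requiring both** (356 and 379 nodes, factor 1.3, excluded nodes behaving like the rest):
- True difference +0.044: SE = √(1.3 × (0.112 - 0.044²)/356) = 0.0200, and 0.094/0.0200 - 1.96 = 2.73, so PP-only power is about 99.7%. The joint rule costs less than 0.1 point by simulation. Power is above 90% because the plan doubles 137 pairs to 274 before inflating.
- True difference 0: SE = 0.0202, and 0.05/0.0202 - 1.96 = 0.51, so PP-only power is about 70%. Joint power by simulation is about 68%.

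**The case against.** Four points can be made for leaving the plan as it is.

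**The direction is unknown.** A reader might infer that PP is biased towards IC2000: 12.3 places enrolment "just prior to the time of injection of IC2000", after Tc-99m has been injected, so it may seem that only the IC2000 dose can fall short. The documents do not support this. The full-dose criterion covers both agents and sets no time point, and the visible eligibility criteria do not require a complete Tc-99m dose. A subject with a short Tc-99m dose can be enrolled, stay in mITT and leave PP, which works against IC2000. This stands, and it limits the point to PP not being guaranteed conservative.

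**The numbers are hypothetical.** No rate of incomplete dosing is given, 23 nodes is a ceiling, and the plan's own figures imply only 3.4% Tc99m-only nodes. The injection section that may define a full dose is not in the public text and is not held against the plan. This also stands.

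**A PP claim is not an error on its own terms.** Suppose the true mITT difference is exactly -5 points and a share f of 23 extra nodes is Tc99m-only. The PP difference is then (-0.05 × 379 + 23f)/356, that is -3.7 points at f = 25% and -2.1 at f = 50%. PP alone would claim non-inferiority about 11% or 38% of the time without the inflation factor, and about 9% or 30% with it. A reader might take these as inflated Type I error. They are that only if mITT is the target population; the PP difference in these cases lies inside the margin. Without the factor they fall to about 6% and 13% with 12 nodes, and about 4% and 6% with 6. They are upper-bound illustrations.

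**Disagreement would be visible.** The mITT analysis is prespecified, and 14.4 will present discordant nodes. That is true, but visibility does not settle which result governs the claim.

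**Conclusion.** The concern holds in a limited form. Non-inferiority status alone does not justify PP as the deciding set here, because an under-dosed tracer shifts the paired difference instead of diluting it. PP may be stricter or more lenient than mITT, and the documents do not say which to expect.

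The practical size depends on where the result falls. At an observed difference near 0, about 4 or 5 Tc99m-only nodes outside PP would split the two sets. At the planned +4.4 points it would take 18 of the maximum 23, and with 12 or fewer extra nodes it could not happen. These counts rest on the plan's discordance and inflation factor, a Wald interval, and the remaining extra nodes being concordant. This is an inexpensive improvement to the decision rule and not a flaw that undermines the design.

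**What to change.** Replace the last sentence of 14.3 with: *Non-inferiority will be claimed if the lower bound of the two-sided 95% confidence interval for the difference exceeds -0.05 in both the PP and the mITT population.* Amend 14.1 so that mITT takes part in this joint decision as well as being reported. The joint rule protects whichever way the exclusions work.

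No alpha adjustment is needed, because both sets must pass. The mITT analysis is already planned, so the change is two sentences. The price is the small power loss shown above when the true difference is near 0. The loss would be larger if the excluded subjects really contain many IC2000 misses, and that is the case the rule is meant to catch.
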